6.5.1. Study Phases

[figure not shown]
The subjects included and the treatment arms considered for statistical analyses and summaries in each phase are described below in this section. The specific summaries are discussed in the following sections.

- Placebo-controlled Phase (Weeks 0 to 16)

The two treatment arms are 30 mg BID or Placebo, all subjects in the ITT population are to be included.

- Apremilast Extension Phase (Weeks 16 to 32)

The two treatment arms are 30 mg BID/30 mg BID, and Placebo/30 mg BID. Subjects included are those in the ITT population who entered the Apremilast Extension Phase, either were initially randomized to 30 mg BID or placebo, respectively.

CCI

6.5.3. Dermatology Life Quality Index (DLQI)

The endpoints include:

- Change from baseline in DLQI total score at Weeks 4, 8, 16 and 32
- Change from baseline in DLQI subscale scores at Weeks 4, 8, 16 and 32

CCI
C
I

Mean change from baseline in DLQI total score and subscale scores will be summarized by treatment group and time point using descriptive statistics. Analysis for the Week 16 change from baseline in DLQI total score is presented in the secondary efficacy endpoint Section 6.4.2.

CCI

Week 16 DLQI

response will be analyzed similarly as the primary and secondary binary endpoint. The treatment difference between apremilast 30 mg BID and placebo will be compared using CMH test adjusting for the stratification factor at randomization. The 2-sided p-values from the CMH test, the adjusted treatment difference in proportion using the weighted average of the treatment differences across the strata with the CMH weights, along with the associated 2-sided 95% CIs using a normal approximation to the weighted average will be provided. The analysis will be based on ITT population with missing values imputed using the LOCF method.

6.5.4. Whole Body Itch and Scalp Itch Numeric Rating Scale (NRS) Assessment

The endpoints include:

- Whole body itch NRS score by visit
- Scalp itch NRS score by visit
- Change from baseline in whole body itch NRS score by visit
- Change from baseline in scalp itch NRS score by visit

All endpoints will be summarized by treatment group and time point using descriptive statistics.

Shift tables for shifts from baseline to post-baseline visits and End of Phase (LOCF) will be provided by treatment and time point for whole body itch NRS score and scalp itch NRS score.

CCI

6.5.6. Scalp Physician Global Assessment (ScPGA) CCI

The endpoints include:

- ScPGA response defined as proportion of subjects with ScPGA score of clear (0) or almost clear (1) with at least a 2-point reduction from baseline by visit

CCI

These endpoints will be summarized by treatment group and time point.

Analysis for the Week 16 ScPGA response is presented as the primary efficacy endpoint in Section 6.3.

CCI

The treatment difference between apremilast 30 mg BID and placebo will be compared using CMH test adjusting for the stratification factor at randomization. The 2-sided p-values from the CMH test, the adjusted treatment difference in proportion using the weighted average of the treatment differences across the strata with the CMH weights, along with the associated 2-sided 95% CIs using a normal approximation to the weighted average will be provided. The analysis will be based on ITT population with missing values imputed using the LOCF method.

Shift tables for CCI and ScPGA shifts from baseline to post-baseline visits and End of Phase (LOCF) will be provided by treatment and time point.

6.6. Subgroup Analysis

Subgroup analyses for ScPGA response at Week 16 and proportions of subjects with ≥ 4 -point reduction (improvement) from baseline in the whole body itch NRS or scalp itch NRS scores at post baseline time points based upon baseline demographic or baseline disease characteristics. Summary and analysis will be based on ITT population and missing values will be imputed using MI method. Treatment-difference for response will be reported with 2-sided 95% CI.

The following subgroup variables will be considered and analyzed when appropriate:

- Sex (Male, Female)
- Race (White, Others)
- Age category (< 65 , ≥ 65)
- Baseline weight (< 85 , ≥ 85 to < 100 , ≥ 100 kg)
- Baseline BMI category (< 25 , ≥ 25 to < 30 , ≥ 30 to < 35 , ≥ 35 to < 40 , ≥ 40 kg/m^2)
- Geographical region (USA, Canada)
- Alcoholic beverage drinking (Yes, No)
- Tobacco use (Current user, Past user, Never used)
- Duration of plaque psoriasis categories (< 10 , ≥ 10 to < 20 , ≥ 20 years)
- Baseline ScPGA score: 3 (moderate), 4 (severe)

- Baseline whole body itch NRS score (0 to 3, 4 to 6, 7 to 10)
- Baseline scalp itch NRS score (0 to 3, 4 to 6, 7 to 10)
- [REDACTED]
- [REDACTED]
- [REDACTED]
- [REDACTED]
- Number of prior conventional systemic therapies (0, ≥ 1)
- Number of prior biologic therapies (0, ≥ 1)
- Number of prior systemic therapies (0, ≥ 1)
- Number of prior topical scalp psoriasis medications or shampoo treatments (1, ≥ 2)
- Number of failed prior scalp psoriasis medications or shampoo treatments for subjects who had prior scalp psoriasis medications or shampoo treatments (0, ≥ 1)

CCI

[REDACTED]

[REDACTED]

[REDACTED]

[REDACTED]

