#### **9.6.1.5. Subgroup Analysis**

Subgroup analyses for ScPGA response at Week 16 and proportions of subjects with  $\geq 4$ -point reduction (improvement) from baseline in the whole body itch NRS or scalp itch NRS scores at post baseline time points based upon baseline demographic (age, gender, race, etc.) or baseline disease characteristics will be provided to determine the robustness of the treatment effect.

CC1 [REDACTED]  
[REDACTED]  
[REDACTED]

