6.3. Analyses of Primary Efficacy Endpoint

The primary endpoint is the proportions of subjects who achieving ScPGA response at Week 16 (defined as ScPGA score of clear [0] or almost clear [1] with at least a 2-point reduction from baseline at Week 16). The primary endpoint will be analyzed using the ITT population. A sensitivity analysis will be performed using the PP population.

The treatment difference between apremilast 30 mg BID and placebo will be compared using CMH test adjusting for the stratification factor at randomization. The 2-sided p-values from the CMH test, the adjusted treatment difference in proportion using the weighted average of the treatment differences across the strata with the CMH weights, along with the associated 2-sided 95% CIs using a normal approximation to the weighted average will be provided ([Mehrotra and Railkar, 2000](#)). Missing values at Week 16 will be imputed using the multiple imputation (MI) method ([SAS Institute Inc. 2011](#)) as the primary analysis, with sensitivity analysis using the last observation carried forward (LOCF) method and the non-responder imputation (NRI) method.

The SAS procedure MI will be used to impute missing ScPGA scores at the scheduled analysis visits in the Placebo-controlled Phase (Weeks 0 to 16) to create M=25 complete data sets. The missing data patterns will be checked by treatment and stratification factor at Baseline (Week 0), and Weeks 2, 4, 8, 12 and 16. If there are non-monotone missing patterns, two separate imputation procedures will be used to complete the imputation process.

In the first step, the Markov Chain Monte Carlo (MCMC) method will be used to impute missing scores by treatment and stratification factor to create M=25 imputed data sets with monotone missing patterns. The minimum and the maximum values for imputation will be 0 and 4, which correspond to the lowest and the highest ScPGA scores. The seed will be set to 804529, the imputed values will be rounded to integers and a single chain will be used to produce imputations. In case there are convergence issues, a simple model will be used to impute the missing scores by treatment, with further simplification by dropping both treatment and stratification factor in imputation model if necessary.

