In the second step, the predictive mean matching method will be used to impute the remaining missing values for the 25 data sets with monotone missing patterns. The MONOTONE REGPMM statement will be used with seed 447159. The missing values at each visit will be imputed based on treatment, stratification factor, and ScPGA scores at baseline and previous visits. The number of closest observations to be used in the selection will be K=2.

After the completion of imputation, the same CMH method will be used to analyze the 25 complete data sets and the SAS procedure MIANALYZE will be used to combine the results for the statistical inferences.

In summary, the primary analysis will be performed for ITT population using the MI method for treating missing values. Supportive analyses will be performed for: (1) ITT population treating missing values using the LOCF method, (2) ITT population treating missing values using the NRI method, (3) PP population using the MI method for treating missing values. In addition, analyses using CMH test adjusting for the stratification factor at randomization and pooled site will be performed for ITT population using MI method for imputing missing values.

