The SAS procedure MI will be used to impute missing whole body itch NRS score (or scalp itch NRS score) at the scheduled analysis visits in the Placebo-controlled Phase (Weeks 0 to 16) to create M=25 complete data sets. The missing data patterns will be checked by treatment and stratification factor at Baseline (Week 0), and Weeks 2, 4, 8, 12 and 16. If there are non-monotone missing patterns, two separate imputation procedures will be used to complete the imputation process.

In the first step, the Markov Chain Monte Carlo (MCMC) method will be used to impute missing scores by treatment and stratification factor to create M=25 imputed data sets with monotone missing patterns. The minimum and the maximum values for imputation will be 0 and 10, which correspond to the lowest and the highest whole body itch NRS score (or scalp itch NRS score). The seed will be set to 804529, the imputed values will be rounded to integers and a single chain will be used to produce imputations. In case there are convergence issues, a simple model will be used to impute the missing scores by treatment, with further simplification by dropping both treatment and stratification factor in imputation model if necessary.

In the second step, the predictive mean matching method will be used to impute the remaining missing values for the 25 data sets with monotone missing patterns. The MONOTONE REGPMM statement will be used with seed 447159. The missing values at each visit will be imputed based on treatment, stratification factor, and whole body itch NRS score (or scalp itch

NRS score) at baseline and previous visits. The number of closest observations to be used in the selection will be K=5.

After the completion of imputation, the same CMH method will be used to analyze the 25 complete data sets and the SAS procedure MIANALYZE will be used to combine the results for the statistical inferences.

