6.9. Assessing Study Site Effect

This multicenter study has approximately 46 study sites. As site enrollment caps are imposed, no single site will have sufficient number of subjects to allow a meaningful within-site analysis of treatment effects stratified by baseline ScPGA score; therefore, study site effect will be assessed by pooling sites on geographic basis to help interpret the results should potential site effect be suspected.

In pooling sites for analysis purposes, a minimum of 5 randomized subjects per treatment group (apremilast 30 mg BID or placebo) per stratum of baseline ScPGA score (moderate [3], or severe [4]) will be used. The pooling strategy is described as follows: 1) Sites will be pooled within

each country (USA or Canada) according to their rank based on site-specific sample size, starting with the smallest sites; i.e., within a country, the smallest sites will first be pooled until the pooled site has a minimum cell size of 5 for each of the four cells. 2) The remaining un-pooled sites will then be pooled within the country with the smallest pooled site. 3) In the rare case that all site pooled together in a country does not satisfy the above condition (a minimum cell size of 5 for each of the four cells), all sites in the country will be pooled together with the smallest pooled site of the other country.

Sites will be pooled together as described above in order to assess the site effect and site by treatment interaction on the primary and major secondary efficacy endpoints as below:

- ScPGA Response: Proportion of subjects with ScPGA score of clear (0) or almost clear (1) with at least a 2-point reduction from baseline at Week 16
- Whole Body Itch NRS Response: Proportion of subjects with ≥ 4 -point reduction (improvement) from baseline in the whole body itch NRS score at Week 16
- Scalp Itch NRS Response: Proportion of subjects with ≥ 4 -point reduction (improvement) from baseline in the scalp itch NRS score at Week 16

For the pooled sites, summary and analyses will be based on ITT population using MI imputation for missing values. Study site effect will be assessed for the primary and the major secondary endpoint by stratifying the analysis based on pooled site in addition to the stratification factor at randomization and examining whether the treatment differences adjusted for both stratification factor and pooled site are consistent with those from the primary analysis.

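### Subgroup and by-site results rest on imputations that omit most of the factors compared, so subgroup differences are pulled modestly toward the overall effect (minor)

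*SAP*

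**What the plan says.** SAP 6.6 lists 17 readable subgroup factors for ScPGA response at Week 16 and for the two itch responses. On missing data it states only that "Summary and analysis will be based on ITT population and missing values will be imputed using MI method". SAP 6.9 has the same for sites: "For the pooled sites, summary and analyses will be based on ITT population using MI imputation for missing values". It then compares the effect across individual or pooled sites treated as subgroups. Neither section describes an imputation model of its own.

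The models described for these endpoints are in SAP 6.3 (ScPGA) and 6.4.1 (itch):

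- **Step 1** is used only where the missing pattern is not monotone: "In the first step, the Markov Chain Monte Carlo (MCMC) method will be used to impute missing scores by treatment and stratification factor". If it fails to converge, it may be simplified to treatment alone, and then "with further simplification by dropping both treatment and stratification factor in imputation model if necessary".
- **Step 2** fills what remains, which includes all data lost to dropout: "The missing values at each visit will be imputed based on treatment, stratification factor, and ScPGA scores at baseline and previous visits". The itch version is parallel, with the itch score in place of ScPGA.

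No product with treatment is listed in step 2. The protocol (9.6.1.5) gives the purpose of the subgroup analyses: they "will be provided to determine the robustness of the treatment effect".

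**The concern.** The subgroup analysis estimates a separate treatment effect at each level of a factor. The imputation for most factors assumes one effect common to all levels. When the imputation model is poorer than the analysis model in this way, a subject with a missing Week 16 score gets a value drawn from donors across all levels of the factor, and each subgroup's difference moves toward the overall one.

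The direction is what matters. These tables exist to show whether the effect is consistent, and the imputation supplies part of the consistency. A subgroup with little benefit would look somewhat closer to the overall result, and more so as missing data increase.

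**Working it through.** **Inputs.** From the documents: 300 subjects, 2:1 (200 and 100); 38% versus 20% response; step 2 by predictive mean matching with K=2 for ScPGA. Assumed, because the documents do not give them: the share missing at Week 16 (10 to 30%), the true subgroup effects, the correlation between visits, and dropout unrelated to outcome.

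**The plan's own figure.** The plan states no figure for heterogeneity or missingness. Its power statement fixes the arm sizes and rates. Pooled rate = (20 + 76)/300 = 0.32; null SE = sqrt(0.32 × 0.68 × (1/100 + 1/200)) = 0.0571; alternative SE = sqrt(0.20 × 0.80/100 + 0.38 × 0.62/200) = 0.0527. Power = Φ((0.18 − 1.96 × 0.0571)/0.0527) = 90.2%, against 90% stated. It reproduces.

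**Approximate ceiling.** Take two equal subgroups with true differences of 28 and 8 points (overall 18, gap 20). If a fraction m is missing with no post-baseline score, and donors ignore the subgroup, the expected subgroup difference is (1 − m) × own + m × overall, so the gap becomes (1 − m) × 20. That is 18, 16 and 14 points at m = 10, 20 and 30%. Earlier scores carry part of the subgroup effect, so subjects who drop out later lose less.

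**Sampling error of the gap.** With 100 apremilast and 50 placebo subjects per half: sqrt(0.20 × 0.80/50 + 0.48 × 0.52/100 + 0.20 × 0.80/50 + 0.28 × 0.72/100) = 0.104, or about 10 points.

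**Simulation of step 2.** 400 trials per setting, 5 imputations each, monotone dropout, same true effects. Gap in points:

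| Missing | Timing of dropout | Full data | Plan's model | Factor + product added | Loss under plan |
|---|---|---|---|---|---|
| 10% | before Week 2 | 20.5 | 18.2 | 20.4 | 11% |
| 10% | spread over visits | 19.3 | 17.9 | 19.3 | 7% |
| 20% | before Week 2 | 19.4 | 15.5 | 19.4 | 20% |
| 20% | spread over visits | 20.7 | 17.6 | 20.6 | 15% |
| 30% | before Week 2 | 19.3 | 13.7 | 19.3 | 29% |
| 30% | spread over visits | 20.5 | 16.5 | 20.3 | 20% |

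Two further simulations with other assumed effects agree:

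- True differences of about 33 and 8 points, CMH-weighted: the gap went from 25.3 to 23.6, 23.9 to 20.6 and 24.4 to 19.4 points at 10, 20 and 30% missing. The share kept was 93, 86 and 80%; the extended model kept 98 to 100%.
- A gap of about 29 points: the loss was about 6% at 10% missing and 12% at 20% (29.0 to 25.4).

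Together: 6 to 11% at 10% missing and 12 to 20% at 20%. On a 20-point gap that is 1.2 to 2.2 points and 2.4 to 4 points.

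**Factors already in the model.** With the factor entered as a main effect only, as baseline ScPGA is in step 2, the loss was about 1 to 3% at 10 and 20% missing.

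**NRI as a check.** If dropout is equal across arms and subgroups and unrelated to response, NRI multiplies every response rate by (1 − m), and so the gap too: 90, 80 and 70% is kept. In the 29-point simulation at 20% missing, NRI gave 23.4 points (0.8 × 29.0 = 23.2), against 25.4 for the plan's MI.

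**The case against.** The case for leaving the plan alone is considerable, and much of it stands.

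- **Size.** At 10% missing, sampling error is several times the bias. In the 29-point simulation, coverage of the plan's intervals stayed near 95%.
- **Precision.** The plan's estimates vary less. At 20% missing before Week 2, the standard deviation of the gap was 9.6 points under the plan and 11.7 with the added terms. Counting the 3.9-point bias, the plan's root mean squared error is sqrt(9.6² + 3.9²) = 10.4, which is below 11.7. The argument for the fix is therefore not accuracy. It is that a check for heterogeneity should not have homogeneity built in.
- **Role.** No subgroup is in the test sequence of SAP 6.2.
- **Feasibility.** About 46 sites in 300 subjects is some 6.5 per site, about 2 of them on placebo. Site-by-treatment terms cannot be fitted for individual sites, and sparse levels such as the top BMI class raise the same problem.
- **Text.** That 6.6 and 6.9 reuse the earlier imputations is the natural reading but is not stated, and material between those sections is blacked out.

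A reader might infer more than the documents support:

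- That every subgroup comparison is affected. Baseline ScPGA is in every model, and step 1 is run by treatment and stratum. Each baseline itch score is in its own itch model, though not in the ScPGA model.
- That the site assessment as a whole is compromised. The CMH analysis adjusted for pooled site estimates one overall difference, which this barely touches. Only the by-site comparison and the stated interest in site-by-treatment interaction are exposed.
- That NRI by subgroup would be a clean check because it borrows nothing across subgroups. It shrinks the gap by about the missing fraction, which is more than the plan's MI does when dropouts have earlier scores.

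**Conclusion.** The point holds in a limited form and is minor. For most listed subgroup factors and for site, the imputation model most naturally inherited has neither the factor nor its product with treatment, so differences between subgroups are understated. The loss is roughly 6 to 11% of the gap at 10% missing and 12 to 20% at 20%. It is systematic and favours apparent consistency, but it is small beside sampling error at plausible sizes. Baseline ScPGA, baseline itch in its own model, the primary result, the sample size and the pooled-site-adjusted estimate are not materially affected.

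The figures rest on assumed missing rates, assumed subgroup effects, two equal halves, and monotone dropout unrelated to outcome. Only the ScPGA step 2 model was simulated. For baseline itch, the conclusion is carried over from the main-effect result.

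**What to change.** State in SAP 6.6 and 6.9 which imputation model applies. In 6.6, and in 6.9 for the comparison across pooled sites, re-run step 2 (MONOTONE REGPMM) for each factor with adequate cell sizes, adding that factor and its product with treatment, after merging sparse levels. Keep the 6.3 and 6.4.1 imputations unchanged for the overall analyses. For factors that stay sparse and for individual sites, show observed-case results alongside instead. Do not add NRI as the check.

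The cost is SAP wording and extra imputation runs, one set per factor and endpoint. Subgroup estimates become somewhat more variable, although the average reported standard error in the 29-point simulation was 0.109 with either model at 20% missing. Subgroup tables would no longer share one imputed data set with the overall analysis and may not add up to it exactly, which a footnote should say. SAP section 2 has the plan finalised before the Week 16 data are unblinded, so the choice can be pre-specified.

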6.9. Assessing Study Site Effect

This multicenter study has approximately 46 study sites. As site enrollment caps are imposed, no single site will have sufficient number of subjects to allow a meaningful within-site analysis of treatment effects stratified by baseline ScPGA score; therefore, study site effect will be assessed by pooling sites on geographic basis to help interpret the results should potential site effect be suspected.

In pooling sites for analysis purposes, a minimum of 5 randomized subjects per treatment group (apremilast 30 mg BID or placebo) per stratum of baseline ScPGA score (moderate [3], or severe [4]) will be used. The pooling strategy is described as follows: 1) Sites will be pooled within

each country (USA or Canada) according to their rank based on site-specific sample size, starting with the smallest sites; i.e., within a country, the smallest sites will first be pooled until the pooled site has a minimum cell size of 5 for each of the four cells. 2) The remaining un-pooled sites will then be pooled within the country with the smallest pooled site. 3) In the rare case that all site pooled together in a country does not satisfy the above condition (a minimum cell size of 5 for each of the four cells), all sites in the country will be pooled together with the smallest pooled site of the other country.

Sites will be pooled together as described above in order to assess the site effect and site by treatment interaction on the primary and major secondary efficacy endpoints as below:

- ScPGA Response: Proportion of subjects with ScPGA score of clear (0) or almost clear (1) with at least a 2-point reduction from baseline at Week 16
- Whole Body Itch NRS Response: Proportion of subjects with ≥ 4 -point reduction (improvement) from baseline in the whole body itch NRS score at Week 16
- Scalp Itch NRS Response: Proportion of subjects with ≥ 4 -point reduction (improvement) from baseline in the scalp itch NRS score at Week 16

For the pooled sites, summary and analyses will be based on ITT population using MI imputation for missing values. Study site effect will be assessed for the primary and the major secondary endpoint by stratifying the analysis based on pooled site in addition to the stratification factor at randomization and examining whether the treatment differences adjusted for both stratification factor and pooled site are consistent with those from the primary analysis.

In addition, the consistency of the treatment effect across individual study sites (or pooled sites) will also be assessed by performing a subgroup-type analysis with respect to the endpoints, with individual study sites (or pooled sites) treated as subgroups (see Section 6.6). Listings of response rates will be provided by individual study site and by pooled site. The treatment difference for each of the individual study sites (or pooled sites) will be reviewed to determine the effect among the individual study sites (or pooled sites).

